8.3.2 Method of Detecting Adverse Events and Serious Adverse Events

At each study visit, the participant will be queried on changes in his or her condition. In addition, the participants will be asked to record AEs in a continuous manner in their patient diary.

Care will be taken not to introduce bias when detecting AEs and/or SAEs. Open-ended and non-leading verbal questioning of the participant is the preferred method to inquire about AE occurrences.

It is important that each AE report include a description of the event, its duration (onset and resolution dates and times when it is important to assess the time of AE onset relative to the recorded treatment administration time), its severity, its causal relationship with cladribine tablets, any other potential causal factors, any treatment given or other action taken, and its outcome. In addition, serious cases should be identified, and the appropriate seriousness criteria documented.

The method of recording, evaluating, and assessing causality of AEs and SAEs and the procedures for completing and transmitting SAE reports are in Appendix 7.

8.3.3 Follow-up of Adverse Events and Serious Adverse Events

After the initial AE/SAE report, the Investigator is required to proactively follow each participant at subsequent visits/contacts. All SAEs will be followed until resolution, stabilization, the event is otherwise explained, or the participant is lost to follow-up (as defined in Section 7.3). Reasonable attempts to obtain this information will be made and documented. It is also the Investigator's responsibility to ensure that any necessary additional therapeutic measures and follow-up procedures are performed. Further information on follow-up procedures is in Appendix 7.

8.3.4 Regulatory Reporting Requirements for Serious Adverse Events

Prompt notification by the Investigator to the Sponsor of an SAE (particularly life-threatening and deaths) is essential so that legal obligations and ethical responsibilities towards the safety of participants and the safety of a study intervention under clinical investigation are met.

The Sponsor has a legal responsibility to notify both the local regulatory authority and other regulatory agencies about the safety of a study intervention under clinical investigation. The Sponsor will comply with country-specific regulatory requirements relating to safety reporting to the regulatory authority, Institutional Review Boards (IRB)/Independent Ethics Committees (IEC), and Investigators.

Individual Case Safety Reports will be prepared for suspected unexpected serious adverse reactions (SUSAR) according to local regulatory requirements and Sponsor policy and forwarded to Investigators, as necessary.

An Investigator who receives an Individual Case Safety Report describing a SUSAR or other specific safety information (e.g., Emerging Safety Issue Report, summary or listing of SAEs/SUSARs) from the Sponsor will review and then file it along with the SmPC in the Investigator's Site File and will notify the IRB/IEC, if appropriate according to local requirements.

8.3.5 Pregnancy

- Details of all pregnancies in female participants will be collected from the signing of the ICF until the last study visit at the time points specified in the Schedule of Activities (Section 1.3).
- If a pregnancy is reported, the Investigator will inform the Sponsor within 24 hours of learning of the pregnancy and will follow the procedures specified below for collection of pregnancy information.
- Abnormal pregnancy outcomes (e.g., spontaneous abortion, fetal death, stillbirth, congenital anomalies, ectopic pregnancy) are considered SAEs.

Collection of Pregnancy Information

Pregnancy relevant information on male participants with female partners will not be collected due to lapse of more than 6 months since the last dose of cladribine tablets.

Female Participants who become pregnant

- The Investigator will collect pregnancy information on any female participant who becomes pregnant while she is in the study. The initial information will be recorded on the appropriate form and submitted to the Sponsor within 24 hours of learning of the pregnancy.
- The participant will be followed to determine the outcome of the pregnancy. The Investigator will collect follow-up information on the participant and the neonate, and the information will be forwarded to the Sponsor. Generally, follow-up will not be required for longer than 6 to 8 weeks beyond the estimated delivery date. Any termination of pregnancy will be reported, regardless of fetal status (presence or absence of anomalies) or indication for the procedure.
- While pregnancy itself is not considered to be an AE or SAE, any pregnancy complication or elective termination of a pregnancy for medical reasons will be reported as an AE or SAE and recorded in the eCRF.
- A spontaneous abortion (occurring at <22 weeks gestational age) or stillbirth (occurring at >22 weeks gestational age) is always considered to be an SAE and will be reported as such.
- Any post-study pregnancy related SAE considered reasonably related to cladribine tablets by the Investigator will be reported to the Sponsor as specified in Section 8.3.4. While the Investigator is not obligated to actively seek this information in former study participants, he or she may learn of an SAE through spontaneous reporting.
- Any female participant who becomes pregnant while participating in the study may continue in the study, as no study intervention is involved, and the assessments are largely part of routine medical care for MS.

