8.3 Adverse Events and Serious Adverse Events

In this section, "study intervention" refers to cladribine tablets (i.e., the study intervention of the MAGNIFY MS parent trial) since no study intervention is administered in this study.

- The definitions of an AE and a SAE are in Appendix 7.
- The Investigator and any qualified designees (e.g., Sub-Investigators) are responsible for detecting, documenting, and recording events that meet the definition of an AE or SAE. The Investigator remains responsible for following up AEs that are serious or that caused the participant to discontinue the study, as specified in Section 8.3.3.
- Requests for follow-up will usually be made via the Study Monitor, although in exceptional circumstances the global patient safety department may contact the Investigator directly to obtain further information or to discuss the event.

8.3.1 Time Period and Frequency for Collecting Adverse Event and Serious Adverse Event Information

- All SAEs will be collected from the signing of the ICF until the last study visit at the time points specified in the Schedule of Activities (Section 1.3). Beyond this reporting period, any new unsolicited SAEs that the Investigator spontaneously reports to the Sponsor will be collected and processed.
- All AEs will be collected from the signing of the ICF until the last study visit at the time points specified in the Schedule of Activities.

- The date of the last procedure according to the parent study protocol (i.e., the parent study exit date) and the date of signing informed consent for the extension study (i.e., the extension study enrollment date) is important to determine how AEs/SAEs should be recorded and reported:
 - Ongoing SAEs and events of lymphopenia (also if not serious) with an onset date
 prior to the parent study exit date will be recorded on the Medical History/Current
 Medical Conditions CRF. If the condition worsens, a new SAE will be recorded on
 the AE CRF page and reported as specified in Appendix 7. Other non-serious AEs
 which are ongoing at the parent study exit date will not be recorded in the extension
 study.
 - AEs/SAEs with an onset date after the parent study exit date and before the extension study enrollment date will be collected retrospectively (after obtaining informed consent) and recorded on the AE CRF page for the extension study.

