Appendix 10 Contraception

According to cladribine tablets (Mavenclad®) SmPC, there are no requirements regarding contraception that apply after 6 months since the last dose. At the time of enrollment in the MAGNIFY MS Extension study, participants will have completed treatment. The treatment start was since minimally 2 years, with minimally 12 months since starting the second year treatment.

Substance code: N/A MS700568_0157

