15.5 Other Safety or Tolerability Evaluations

The results of the physical examination will not be presented in any statistical analysis or listing. Abnormalities occurring, or worsening, during the study will be reported as AE.

Pregnancies reported as AEs or SAEs will be listed for the SAF.

16 Analyses of Other Endpoints

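### SAP 15.5 lists only pregnancies reported as AEs or SAEs, and gap-period pregnancies are not named for collection, so the pregnancies shown are selected by complication or outcome and have no denominator

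*Protocol*

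**What the plan says.** Collection. Protocol Section 8.3.5: "Details of all pregnancies in female participants will be collected from the signing of the ICF until the last study visit". The same section adds "The Investigator will collect pregnancy information on any female participant who becomes pregnant while she is in the study" and "The participant will be followed to determine the outcome of the pregnancy". Notification goes to the sponsor within 24 hours, and Appendix 7 specifies a separate paper form for it.

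Classification. Protocol 8.3.5: "While pregnancy itself is not considered to be an AE or SAE". Complications, and elective terminations for medical reasons, are AEs or SAEs and go into the eCRF. "Abnormal pregnancy outcomes (e.g., spontaneous abortion, fetal death, stillbirth, congenital anomalies, ectopic pregnancy) are considered SAEs".

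Gap period. For participants whose Extension Baseline falls after the parent study's last visit, Protocol Section 8.3.1 has a separate rule: "AEs/SAEs with an onset date after the parent study exit date and before the" extension enrollment date are collected retrospectively. The gap items named in Protocol Section 4.1 and under the Baseline visit in Section 8 are EDSS, relapses, AEs/SAEs and concomitant medications. Pregnancy is not among them.

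Reporting. SAP Section 15.5: "Pregnancies reported as AEs or SAEs will be listed for the SAF". No count, table or outcome summary of all pregnancies is visible elsewhere in the SAP. SAP Section 15 bases safety analyses on the Extension Study Period, which SAP Section 9.6 starts on the day after the Month 24 visit ends. The gap therefore lies inside the safety period.

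**The concern.** The protocol asks for every pregnancy after consent and for its outcome. The SAP then uses AE or SAE status to decide which ones are shown, although the protocol says that pregnancy alone has no such status. A reader of the study report would see complications, medically indicated terminations and abnormal outcomes, with no statement of how many pregnancies there were.

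For gap participants the selection starts earlier, at collection, because the retrospective rule reaches AEs and SAEs but not pregnancies as such.

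At stake is the interpretability of a small part of the long-term safety objective. A few abnormal outcomes mean one thing if there were few pregnancies and another if there were many.

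**Working it through.** The documents state no pregnancy count or rate, so there is no figure to reproduce. The check follows each kind of pregnancy through the written rules.

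| Pregnancy | Collected? | In the SAP 15.5 listing? |
|---|---|---|
| Begins after consent, uncomplicated | Yes: form, followed to outcome (8.3.5) | No: not an AE or SAE |
| Begins after consent, with complication, medical termination or abnormal outcome | Yes: form and AE/SAE (8.3.5) | Yes |
| In the gap, ended before consent, uncomplicated | No rule names it | No |
| In the gap, ended before consent, with complication, medical termination or abnormal outcome | Yes: as a retrospective AE/SAE (8.3.1) | Yes |
| Begins in the gap, ongoing at consent, uncomplicated | Ambiguous | No |

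The fifth row is ambiguous because 8.3.5 speaks both of all pregnancies from consent onward, which can include one already under way, and of a participant who becomes pregnant while in the study, which can exclude it.

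**Reporting step.** Let N be all pregnancies in the Extension Study Period and a those reported as an AE or SAE. The listing shows a. N appears in no visible output, so a/N cannot be read from the report. Any uncomplicated pregnancy makes N larger than a. This holds whatever the numbers and needs no assumption beyond the written rules.

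**Collection step.** Suppose the SAP were changed to count every collected pregnancy, with the collection rule left alone. Let p be the true share with a complication, medical termination or abnormal outcome, and g the share of uncomplicated pregnancies missed because they ended in the gap. The share among collected pregnancies would be

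p / [p + (1 − p)(1 − g)].

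Both p and g are assumptions:

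- g = 0: 10%, 20% and 30% stay 10%, 20% and 30%.
- g = 0.10: 0.10/0.91 = 11.0%; 0.20/0.92 = 21.7%; 0.30/0.93 = 32.3%.
- g = 0.25: 0.10/0.775 = 12.9%; 0.20/0.80 = 25.0%; 0.30/0.825 = 36.4%.

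The error can only be upward, and it is zero if nobody has a gap.

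**How large g could be.** Extension Baseline must precede Visit 1, which is planned at 360 days with a 30-day window (SAP 9.5), so the planned gap is at most 360 + 30 = 390 days. Take an uncomplicated term pregnancy as about 270 days (assumption). To begin and end inside the gap, it must start in the first 360 − 270 = 90 days of a 360-day gap, or the first 390 − 270 = 120 days of a 390-day gap. In a gap shorter than about 270 days it would still be ongoing at consent, which is the ambiguous row. A large g is therefore unlikely for term pregnancies, and the reporting step is the more important of the two.

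**The case against.** The strongest reply is that the safety endpoint is AEs and SAEs, that pregnancy is not an endpoint, and that the SAP listing matches the endpoint. The study is single-arm and exploratory, and no proportion of abnormal outcomes is planned. All of this is correct and limits the severity. It does not explain why data that the protocol requires, follows to outcome and sends to the sponsor should have no planned output.

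It could also be said that sites may in practice enter every pregnancy on the AE page, which would complete the listing for pregnancies that are collected. That would contradict Protocol 8.3.5, so the plan cannot rely on it.

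A reader might infer four stronger things that the documents do not support:

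- That uncomplicated pregnancies are never collected. After consent they are, and each is followed. They are missing only from the output.
- That all gap pregnancies are lost. Those with a complication, a medical termination or an abnormal outcome enter as retrospective AEs or SAEs.
- That the gap holds the pregnancies nearest to dosing. The parent study's last visit is planned 12 months after the second-year course began, or 24 months after the first if there was no second (Protocol 4.1). Appendix 10 says "there are no requirements regarding contraception that apply after 6 months since the last dose", and the gap begins after that period. Pregnancies nearer to dosing belong to the parent study, whose procedures are not in these documents.
- That the length of a gap as a share of follow-up measures the loss, or that everything listed must be an abnormal outcome. The first is calendar time, not lost pregnancies. The second fails because a complicated pregnancy with a healthy birth also qualifies for the listing.

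**Conclusion.** The point holds in two parts.

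First, SAP 15.5 is narrower than Protocol 8.3.5. Uncomplicated pregnancies that are collected appear in no visible output, so the pregnancies that are shown have no denominator. This follows from the wording alone.

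Second, for gap participants only, collection itself depends on complication or outcome, and the status of an uncomplicated pregnancy ongoing at consent is unclear. The size of this part cannot be stated, because the numbers of gap participants, gap lengths and pregnancies are not given. Its direction is toward overstating the share with problems, and it is probably small for term pregnancies under the 270-day assumption.

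No endpoint and no planned estimate changes. Severity is low to moderate: the pregnancy listing cannot be interpreted as planned, and the remedy is simple.

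**What to change.** **SAP 15.5.** List and count all pregnancies in the Extension Study Period, taken from the pregnancy form, with outcome and time since the last cladribine dose. Flag those that were also reported as an AE or SAE.

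**Protocol 8.3.5.** Align the start of collection with the gap rule of 8.3.1. Record pregnancies after the parent study exit date retrospectively at Extension Baseline, add pregnancy to the gap items in Sections 4.1 and 8, and state that pregnancies ongoing at consent are included.

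**Cost.** The text changes are short, and there is one more question at Extension Baseline for gap participants. If Extension Baseline visits are already complete, the gap question would have to be asked at a later contact; the SAP change can still be made without new data for pregnancies collected after consent. Two downsides remain. Gap pregnancies depend on recall, as gap AEs already do. And because the pregnancy form is on paper and goes to the sponsor separately (Appendix 7), while the final analysis uses the locked database (SAP 6.2), the form's data must be transferred to or reconciled with that database before lock.

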8.3.6 Disease-Related Events and/or Disease-Related Outcomes Not Qualifying as AEs or SAEs

The following disease-related events are common in participants with highly-active RMS and can be serious/life threatening:

• Symptoms and signs of relapse or worsening of MS

Because these events are typically associated with the disease under study, they will not be reported according to the standard process for expedited reporting of AEs and SAEs even though the event may meet the definition of an AE or SAE. These events will be recorded on the relapse module of the eCRF page within 15 days after the visit.

However, if either of the following conditions applies, then the event will be recorded and reported as an SAE (instead of a disease-related event):

• The event is, in the Investigator's opinion, of greater intensity, frequency, or duration than expected for the individual participant (i.e. worsening not consistent with the anticipated natural progression of the disease).

[figure not shown]
OR

• The Investigator considers that there is a reasonable possibility that the event was related to study intervention.

8.4	Treatment of Overdose
Not applicable.	
8.5	Pharmacokinetics
Not applicable.	
8.6	Pharmacodynamics
Not applicable.	
CCI	
001	
CCI	

8.9	Immunogenicity Assessments
Not applicable.	
rvot apprication.	
 	
0.4	
9.1	Statistical Hypotheses
No formal statistical	hypothesis will be tested, as the study is designed to be exploratory.
CCI	

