8.1.3 Relapses

In this protocol, symptoms and signs of relapse or worsening of MS since the previous visit will usually be captured in the context of the efficacy assessment and recorded on the relapse module of the eCRF. Therefore, symptoms, relapses or worsening of MS will not be considered as adverse events (AEs) nor captured on the AE module of the eCRF unless considered possibly or probably related to cladribine tablets (i.e. worsening is not consistent with the anticipated natural progression of the disease).

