- New conditions detected or diagnosed after study intervention administration even though it may have been present before the start of the study. However, as the study intervention (cladribine tablets) was administered during the parent study, only new conditions not detected/diagnosed during the parent study need to be collected.
- Signs, symptoms, or the clinical sequelae of a suspected drug-drug interaction.
- Signs, symptoms, or the clinical sequelae of a suspected overdose of either study intervention or a concomitant medication.
- "Lack of efficacy" or "failure of expected pharmacological action" per se will not be reported as an AE or a SAE. However, the signs, symptoms, and/or clinical sequelae resulting from lack of efficacy will be reported as an AE or a SAE if they fulfill the definition of an AE or SAE.

Events NOT Meeting the AE Definition

Unless judged by the Investigator to be more severe than expected for the participant's
condition, any clinically significant abnormal laboratory findings, other abnormal safety
assessments that are associated with the underlying disease, the disease/disorder being
studied, or expected progression, signs, or symptoms of the disease/disorder being
studied.

- Medical or surgical procedure (e.g., endoscopy, appendectomy): the condition that leads to the procedure is the AE.
- Situations in which an untoward medical occurrence did not occur (social and/or convenience admission to a hospital).
- Anticipated day-to-day fluctuations of pre-existing disease(s) or condition(s) present or detected at the start of the study that do not worsen.

AE/SAEs Observed in Association with Disease Progression

Progression of the disease/disorder being studied assessed by measurement of lesions on radiographs or other methods as well as associated clinical signs or symptoms (including laboratory abnormalities) will not be reported as AEs/SAEs, unless the participant's general condition is more severe than expected for the his/her condition and/or unless the outcome is fatal within the AE reporting period, as defined in Section 8.3.1.

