Symptoms and signs of relapse or worsening of MS since the previous visit will usually be captured in the context of the efficacy assessment, and recorded on the relapse module of the eCRF. Therefore, symptoms, relapses or worsening of MS will not be considered as AEs unless considered possibly or probably related to cladribine tablets (i.e. worsening is not consistent with the anticipated natural progression of the disease).

SAE Definition

If an event is not an AE per the definition above, then it cannot be an SAE even if serious conditions are met (e.g., hospitalization for signs/symptoms of the disease under study, death due to progression of disease).

A SAE is defined as any untoward medical occurrence that, at any dose:

a. Results in death

b. Is life-threatening

The term 'life-threatening' in the definition of 'serious' refers to an event in which the participant was at risk of death at the time of the event. It does not refer to an event, which hypothetically might have caused death, if it were more severe.

c. Requires inpatient hospitalization or prolongation of existing hospitalization

• In general, hospitalization signifies that the participant has been detained (usually involving at least an overnight stay) at the hospital or emergency ward for observation and/or treatment that would not have been appropriate in the physician's office or outpatient setting. Complications that occur during hospitalization are AEs. If a complication prolongs hospitalization or fulfills any other serious criteria, the event is serious. When in doubt as to whether "hospitalization" occurred or was necessary, the AE will be considered serious.

- Hospitalization for elective treatment of a pre-existing condition that did not worsen from baseline is **not** considered an AE.
- However, all events leading to unplanned hospitalizations or unplanned prolongation of an elective hospitalization (i.e., undesirable effects of any administered treatment) must be documented and reported as SAEs.

d. Results in persistent disability/incapacity

The term disability means a substantial disruption of a person's ability to conduct normal life functions.

This definition is **not** intended to include experiences of relatively minor medical significance such as uncomplicated headache, nausea, vomiting, diarrhea, influenza, and accidental trauma (e.g., sprained ankle) which may interfere with or prevent everyday life functions but do not constitute a substantial disruption.

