The 6MCDP during Extension Study Period is defined as sustained increase in EDSS score that started during the Period. A Sustained Increase in EDSS score is defined by an increase of:

- at least 1.5 points if the Baseline EDSS score was 0, or
- at least 1 point if Baseline EDSS score was between 0.5 and 4.5 inclusively, or
- at least 0.5 point if the Baseline EDSS score was at least 5,

that occurs over a 6-months' time-period.

The increase will be defined as sustained when it occurs on two post-Baseline Visits during the Extension Study Period that are at least 166 days apart (to be consistent with the parent study minimum visit gap) and no observations at any other visits (including unscheduled visits) in between are less than the defined increase. The assessment date of the earlier of the two EDSS assessments with the defined increase will be defined as the start date of 6MCDP.

For descriptive summaries the following rules will be defined:

Qualifying Relapse

- Yes: any qualifying relapse reported during the Extension Study Period,
- No: Extension study period completed, and no qualifying relapse reported during the Extension Study Period,
- Unknown: otherwise.

6MCDP

• Yes: sustained increase in EDSS score that started during the Extension Study Period,

- No: at least 2 post-Baseline EDSS assessments that are 166 (or more) apart and no sustained EDSS progression that started during the Extension Study Period,
- Unknown: Otherwise.

MRI activity

- Yes: any T1-Gd+ or active T2 observed during the Extension Study Period,
- No: at least one post-Baseline MRI and no T1-Gd+ or active T2 observed during the Extension Study Period,
- Unknown: otherwise.

Analysis (Analysis Set)	Derivation	Statistical Analysis Methods	Missing data handling		
	Primary endpoint: Proportion of participants with NEDA-3 during Year 3 Visit and Year 4 Visit Period after the initial dose of cladribine tablets				

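### Protocol 8.3.6 makes some relapses SAEs with no seriousness test, in conflict with 8.1.3 and Appendix 7, and does not say that they must also stay on the relapse module

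*Protocol*

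**What the plan says.** **Protocol 8.3.6.** The default for relapse or worsening of MS is "These events will be recorded on the relapse module of the eCRF page within 15 days after the visit", outside expedited reporting. Under either of two exceptions, "then the event will be recorded and reported as an SAE (instead of a disease-related event". The first exception is an event that the investigator considers "of greater intensity, frequency, or duration than expected for the individual participant". The second reads "The Investigator considers that there is a reasonable possibility that the event was related to study intervention". Neither mentions a seriousness criterion.

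**Protocol 8.1.3**, repeated almost unchanged in Appendix 7. Relapses usually go on the relapse module and are not AEs "unless considered possibly or probably related to cladribine tablets (i.e. worsening is not consistent with the anticipated natural progression of the disease". The consequence of the exception is an AE.

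**Protocol Appendix 7.** An event is serious when at least one listed criterion is met; a severe rating is not enough. Causality has two levels, related and unrelated. Disease progression is not reported unless the participant's condition is more severe than expected and/or "unless the outcome is fatal within the AE reporting period". The SAE definition then opens with "If an event is not an AE per the definition above, then it cannot be an SAE even if serious conditions are met" and gives death from disease progression as one example.

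**SAP 14.1.1.** The relapse component of NEDA-3 is positive for "any qualifying relapse reported during the Extension Study Period". It is negative if the participant completed the period and none was reported. No eCRF form is named as the source.

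**The concern.** Two things are at stake.

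- **Safety endpoint.** Occurrence of SAEs is a named secondary endpoint (Protocol Section 3, SAP Section 5). If sections of one protocol classify the same relapse differently, the SAE count partly reflects which section the site used. The reporting clock changes too: 24 hours for an SAE (Protocol 8.3.1) against 15 days after the visit for a relapse-module entry.
- **Efficacy endpoints.** The relapse module is where Protocol 8.1.3 places relapse data. If a site treats the SAE record as a substitute for that entry, a qualifying relapse may never reach the efficacy data. Any such loss runs in one direction: NEDA-3, time to first qualifying relapse and the mean cumulative function (MCF) of relapses would all look better than they are.

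**Working it through.** The plan states no figure on this point, so there is none to reproduce. The check is a comparison of texts, followed by a scale calculation.

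**1. The rules side by side**

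| | 8.3.6 | 8.1.3 and Appendix 7 (relapse text) | Appendix 7 (seriousness and causality) |
|---|---|---|---|
| Trigger | Beyond expectation for the participant, OR reasonably possibly related | Possibly or probably related | Related or unrelated only |
| Outcome | SAE | AE | SAE only if a listed criterion is met |
| Seriousness test | None stated | None stated (outcome is an AE) | Required |

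The remark about natural disease progression is attached to relatedness in 8.1.3 and Appendix 7, but to the beyond-expectation trigger in 8.3.6.

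**2. Two test cases, neither meeting a seriousness criterion**

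- *Relapse judged related.* 8.3.6 gives an SAE. 8.1.3 and Appendix 7 give a non-serious AE.
- *Relapse longer than expected, judged unrelated.* 8.3.6 gives an SAE. Under 8.1.3 it is a relapse-module entry only if relatedness decides, or an AE if the site relies on the natural-progression remark.

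**3. Fatal progression.** One Appendix 7 paragraph makes a fatal outcome an exception to non-reporting. The next heading uses death from progression to illustrate what cannot be an SAE. The second statement applies only to events that are not AEs, so the two can be reconciled, but the example points the other way.

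**4. Routing.** 8.3.6 uses the same verb, record, for the relapse module (default) and for the SAE (exception). Replacement is thus a fair literal reading. No visible sentence requires both entries.

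**5. What the SAP would do with an unrecorded relapse.** In the descriptive rules of SAP 14.1.1, a completer with no reported relapse is classed as No, not Unknown. In the Kaplan-Meier analysis, a participant with no other event is censored at the earliest of last MRI, last EDSS and study completion or discontinuation. The crude-percentage analysis in SAP 14.1.2 plans no separate source. None of these would reveal the loss.

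**6. Scale.** N = 200 to 220 evaluable participants (Protocol 1.1). Let k be the number whose only NEDA-3 event is an unrecorded relapse. Ignoring censoring, the shift is k/N.

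| k | N=200 | N=220 |
|---|---|---|
| 1 | 1/200 = 0.50 points | 1/220 = 0.45 points |
| 5 | 2.5 points | 2.27 points |
| 10 | 5.0 points | 4.55 points |

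The values of k are illustrations; the documents give none.

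For comparison, the 95% half-width is 1.96 × √(p(1−p)/N). With p assumed between 0.4 and 0.7, it is 6.35 to 6.93 points at N=200 and 6.06 to 6.61 points at N=220. A shift equal to the half-width needs k of 12.7 to 13.9 (0.0635 × 200 to 0.0693 × 200) or 13.3 to 14.5 (0.0606 × 220 to 0.0661 × 220).

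A participant who also has MRI activity or 6MCDP still counts as a NEDA-3 event, perhaps at another date. That does not protect time to first qualifying relapse or the relapse MCF, which use relapses alone.

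**The case against.** The strongest reply concerns routing. The words in parentheses in 8.3.6 replace a safety class, a disease-related event, and do not mention the relapse module. The Schedule of Activities lists relapse reporting at Baseline, Visit 1, Visit 2 and unscheduled visits, with no exemption for relapses that are also SAEs. Protocol 8.1.3.1 defines a qualifying relapse by clinical criteria alone. Form-level rules may also sit in the eCRF completion instructions or data management documents, which are not available here. All of this stands: loss of relapse records is a risk left open, not a stated rule.

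A reader might go further and infer that the worst relapses are removed from the primary endpoint. The documents do not support that. One trigger is relative to what is expected for the individual and the other is relatedness at any severity. The SAP 6.1 relapse report expects steroid-treated and hospitalised relapses in the relapse data. A reader might also put a total on the bias, but the documents supply neither a relapse rate nor a rate of exception events. Nor does Appendix 7 flatly bar fatal progression from being an SAE, because its statement is conditional.

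It is fair to add that the study is exploratory with no hypothesis test, and that an SAE without a seriousness test errs towards over-reporting. Neither point removes the contradiction in SAE classification. The confidence interval also does not allow for a one-directional recording loss.

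**Conclusion.** The SAE contradiction is established from the text alone. 8.3.6 yields an SAE without a seriousness criterion and on two triggers; 8.1.3 and the Appendix 7 relapse text yield an AE on one; and Appendix 7 requires a criterion for seriousness. Its effect on the SAE count cannot be sized, because the documents do not say how many relapses would meet an exception.

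The routing point holds as an ambiguity without a visible safeguard. Its size is about 0.45 to 0.5 percentage points of NEDA-3 for each participant whose only event is lost, upward in every case. This rests on N of 200 to 220, no censoring before the end of the period, and the relapse module being the source of the relapse component. The last is a reasonable inference from Protocol 8.1.3 that SAP 14.1.1 does not state. The number lost may be zero.

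This should be fixed, but it does not by itself undermine the study.

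**What to change.** 1. **Protocol 8.1.3, 8.3.6 and Appendix 7.** Reconcile the triggers, the causality wording (against the two-level scale) and the AE or SAE outcome, including whether a seriousness criterion must be met. Reconcile the two Appendix 7 statements on fatal progression.
2. **Protocol 8.3.6.** State that every suspected relapse is entered on the relapse module, whatever its AE or SAE status.
3. **SAP 14.1.1.** Name the eCRF form that supplies qualifying relapses. Before database lock, compare AE-page events coded as MS relapse or worsening with the relapse module, and count those that meet Protocol 8.1.3.1 as qualifying relapses.

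The cost is minor rewording and one listing at the Data Review Meeting, with no new procedure. SAP version 2.0 is dated 5 October 2023 and the last visit was planned for Q4 2023 (Protocol 4.1). Protocol rewording at that stage could change little of the data entry, so the reconciliation listing does most of the work for the endpoints.
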